### 11.5 Hypothesis Testing and Operating Characteristics for Correlative-Study Endpoints

Correlative studies will assess antitumor activity measured by levels of biomarker expression. This will involve measurement of the following biomarkers from tumor tissue using RPPA: EGFR, pEGFR, Src, pMAPK, STAT3, pSTAT3, pSTAT5, pSTAT1, pAKT, p38, p21, p27, PARP, E-cadherin, p-ErbB3, and Ki67. In some instances immunohistochemical staining of selected proteins will be performed to verify or validate RPPA results. Biomarkers will be tested for treatment-associated modulation (i.e., change from baseline) as well as for association with 1-year locoregional PFS (primary endpoint), and other efficacy parameters, such as objective response rate, PFS, and overall survival. These analyses will be exploratory in nature.

To estimate the power of our study to assess whether significant modulation of biomarkers occurs from therapy, we assume that 80% of patients in phase II will have a 2nd biopsy after 2 doses of cetuximab with EGFR AS, thereby providing paired tumor tissue samples in 24 patients total. Based on data from a prior phase I clinical trial, the standard deviation was 0.7 on average for paired differences ( $\log_2[\text{post}/\text{baseline}]$ ) in proteins measured pre and post therapy. Assuming this standard deviation will apply, a two-tailed signed rank test at  $\alpha = 0.01$  (to control the false-positive rate) in 24 patients will provide 80% power to detect a change of 0.55 ( $\log_2$  scale), which corresponds to a change of ~46% from the baseline-expression level. Although the search for individual biomarkers that change with treatment is exploratory and hypothesis generating, we will report all nominal p-values along with those that remain significant using a 10% false discovery rate.

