It is also of interest to assess whether biomarker modulation within the treatment window is associated with PFS. To estimate power for these analyses, we use Cox proportional hazards regression to evaluate whether PFS depends on change in biomarker expression, considered for each biomarker individually. We assume that 25% of treated patients will have loco-regional progression within 1 year, i.e., PFS = 0.75, based on expectation averaged over the null and alternative hypotheses. We also assume that among 31 patients enrolled in phase II, 24 will have adequate tissue and biomarker assessments before and after therapy. We further assume that accrual in phase II will take 18 months, with 12 months of follow-up beyond the last patient enrolled. Under exponential survival, these assumptions imply that 9 of the 24 patients with pre-post biomarker measurements will have loco-regional progression within our study time frame. A two-tailed Cox-regression test of trend at  $\alpha = .05$  will therefore have 80% power to detect a hazard ratio of 3.8, which corresponds to a one-unit change (i.e., 2-fold increase or decrease) in the biomarker tested.

With respect to assessing PFS in relation to baseline measurements of biomarkers, we assume that all 31 patients enrolled in study will have tissue available for analysis, in which case 12 patients are expected to have loco-regional progression within the study time frame. For this

situation, the minimum detectable hazard ratio would be 3.2 under the conservative assumption that variability in biomarker expression among patients is no greater than that within patients (greater variability would provide increased opportunity to detect biomarker effects).

The analyses of the correlative data are exploratory. A less restrictive test ( $\alpha = .05$ ) is used for PFS to avoid missing important leads. Nominal p-values for all biomarkers associated positively or negatively with PFS will be reported along with a designation of those that fall within a 10% false discovery rate.

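### Section 11.5 states 80% power for the biomarker–PFS Cox tests at hazard ratios of 3.8 and 3.2; with a roughly normal marker, simulated power is about 70% and 73%.

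*Combined protocol and SAP*

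**What the plan says.** Section 11.5 plans two sets of exploratory PFS analyses, one biomarker at a time, with a two-sided alpha of 0.05.

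- **Biomarker change.** Of 31 phase II patients, "24 will have adequate tissue and biomarker assessments before and after therapy", and 9 of these are expected to progress locoregionally. The method is given as "A two-tailed Cox-regression test of trend". On these event numbers, the plan says, it "will therefore have 80% power to detect a hazard ratio of 3.8, which corresponds to a one-unit change", one unit being a doubling or halving of expression.
- **Baseline biomarker.** All 31 patients contribute, with 12 expected events. Here "the minimum detectable hazard ratio would be 3.2 under the conservative assumption". The assumption concerns spread, namely: "variability in biomarker expression among patients is no greater than that within patients". Power is not restated; 80% is carried over from the preceding paragraph.

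The only information on spread is in the paragraph on modulation: "the standard deviation was 0.7 on average for paired differences" on the log2 scale. The section gives no shape for the marker distribution, no power formula, no mention of simulation, and no choice among the Wald, score and likelihood-ratio forms of the Cox test.

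**The concern.** The two hazard ratios look like output of the usual events formula for a continuous covariate. That formula takes the marker's variance among patients still at risk to be the same at every event. This is accurate near a hazard ratio of 1. At 3 to 4 per unit, patients at the high-risk end of the marker fail first, the spread among those remaining shrinks, and each later event carries less information. Power should then fall short of the formula's value.

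The stake is modest but real. Section 11.5 chooses the looser alpha for PFS so that leads are not missed, which makes the false-negative rate the property of interest. If power is 70% and 73%, that rate is about 30% and 27%, not 20%, at the effect sizes quoted.

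**Working it through.** **Inputs, all from Section 11.5:** two-sided alpha 0.05; power 80%; SD 0.7 for change, and 0.7 for baseline by the equal-variability assumption; 24 patients with 9 events; 31 patients with 12 events; 1-year PFS 75%; exponential survival; 18 months' accrual and 12 months' further follow-up.

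**1. Event counts.** With L = −ln(0.75) = 0.2877 per year and follow-up uniform from 1 to 2.5 years,
P(event) = 1 − [exp(−L) − exp(−2.5L)]/(1.5L) = 0.391.
This gives 24 × 0.391 = 9.4 and 31 × 0.391 = 12.1, so the plan's 9 and 12 reproduce.

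**2. Hazard ratios.** The formula is D = (1.96 + 0.84)² / (SD² × (ln HR)²), so HR = exp[2.80 / (0.7 × √D)].
- D = 9: HR = 3.80. Power at 3.8 is Φ(0.7 × 3 × 1.335 − 1.96) = Φ(0.84) = 80.1%.
- D = 12: HR = 3.18. Power at 3.2 is Φ(0.7 × 3.464 × 1.163 − 1.96) = Φ(0.86) = 80.5%.

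Both stated figures reproduce. A one-sided test would give 3.27 and 2.79, and an evenly split binary marker 6.5 and 5.0, so those variants are not the source.

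**3. Simulation of the Cox test.** 20,000 trials per setting, marker normal with mean 0 and SD 0.7 (normality is an assumption), hazard proportional to HR^x, two-sided 0.05.

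| Setting | HR 3.8, n = 24 (score / LR / Wald) | HR 3.2, n = 31 (score / LR / Wald) |
|---|---|---|
| Exactly 9 or 12 events | 0.70 / 0.72 / 0.68 | 0.73 / 0.74 / 0.72 |
| Expected events 9 or 12, plan's accrual and follow-up | 0.70 / 0.71 / 0.67 | 0.72 / 0.74 / 0.71 |
| Population 1-year PFS 75% | 0.68 / 0.70 / 0.66 | 0.71 / 0.72 / 0.69 |
| 1-year PFS 75% at the mean marker value | 0.75 / 0.76 / 0.73 | 0.76 / 0.77 / 0.75 |

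The last row implies 10.3 and 13.1 expected events, more than the plan's 9 and 12. Rejection under the null was 5.0–6.0%, so a conservative test does not explain the shortfall.

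**4. Cause.** Mean marker variance in the risk set per event was 0.413 and 0.423, against the assumed 0.7² = 0.49. Putting these into the power formula gives Φ(√(9 × 0.413) × 1.335 − 1.96) = Φ(0.61) = 73% and Φ(√(12 × 0.423) × 1.163 − 1.96) = Φ(0.66) = 75%. Lost spread thus accounts for most of the gap. With 90 events and HR 1.52, where the formula also gives 80%, simulated power is 78%.

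**5. Hazard ratio for about 80% power** (normal marker, plan's event counts).
- Change: at 4.4, score 0.77, LR 0.79, Wald 0.75; at 4.8, 0.81, 0.82, 0.79. Roughly 4.5–5.0, depending on the test.
- Baseline: at 3.5, 0.78, 0.79, 0.77; at 3.8, 0.82, 0.83, 0.81. Roughly 3.6–3.8.

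**6. Other marker shapes, SD 0.7.**
- Symmetric (uniform, two-point, t with 5 df), score or LR test: about 64–72% at HR 3.8 and 68–74% at HR 3.2. The Wald test with a two-point marker is much lower, 40% and 59%.
- Strong right skew towards higher hazard (gamma, shape 2): about 77–82% across the two analyses.
- Strong left skew (the mirror image): about 38–60%.

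**The case against.** The strongest reply is that nothing was miscalculated: event counts, SD, alpha and hazard ratios agree with one another under a standard formula, and the section presents them as planning estimates. That stands. This is an approximation used outside its accurate range, not a slip of arithmetic, and the formula itself is inferred from the match.

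It is also fair that the simulated figures need a distribution the plan does not supply. The 16 listed markers need not share one shape, and the association may run in either direction. The 24 pairs, the SD and the 75% PFS are planning guesses too, and the section itself notes that more variability between patients would help detection. So 70% and 73% are conditional figures, and a single replacement number without its assumption would be falsely precise.

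Three stronger readings are tempting and are not supported:

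- *No assumption reaches 80%.* Strong right skew does: the score test gives about 0.80 and 0.82.
- *The likelihood-ratio test always loses least.* It does for the symmetric shapes tried, but under right skew the score test has more power.
- *The trial would take a non-significant marker as evidence against a hazard ratio of 3.8.* Section 11.5 contains no such rule. It calls the analyses exploratory and reports nominal p-values for associated markers, designating those within a 10% false discovery rate.

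Finally, the 31 patients come from the primary endpoint in Section 11.1, and no decision in the plan turns on these tests. That limits the weight of the point but does not make the stated power correct.

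**Conclusion.** The point holds as a minor correction to stated figures. For a roughly normal marker with SD 0.7 and the plan's own event counts, power is about 70% (0.68–0.72 by test) at HR 3.8 and about 73% (0.72–0.74) at HR 3.2, a shortfall of some 7 to 10 percentage points. The assumed marker shape matters more than the choice among the three tests does for a normal marker: symmetric shapes give about 64–74% with a score or likelihood-ratio test, while strong skew can bring power up to the stated 80% or cut it to around half. The 80% at HR 3.2 is implied rather than stated.

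**What to change.** In Section 11.5, replace the two power statements with figures from simulation of the Cox test. Give either the power at the quoted hazard ratios (about 70% at 3.8 and 73% at 3.2) or the hazard ratios detectable with about 80% power (roughly 4.5–5.0 for change and 3.6–3.8 for baseline). Name the form of the Cox test, state the marker distribution assumed, and add a short note that skewed markers would have materially higher or lower power.

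The cost is a few sentences and somewhat less favourable figures. Sample size, design and analysis methods are unchanged.

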## 11.6 Additional Analyses

The data from all evaluable patients will be used in the analyses of safety (phase I and phase II), tumor response (phase II), and survival (phase II).

### Baseline Characteristics

Baseline descriptive statistics on all evaluable patients will be provided on demographic variables (age, sex, and race/ethnicity), performance status, laboratory parameters, treatment regimens that were previously used, and disease characteristics, including tumor size, number of nodes involved, and metastatic sites.

### Safety Profile

Using NCI CTCAE (v4.0), the number of patients experiencing AEs over their course of treatment, and for 30 days beyond the last protocol treatment administered, will be characterized by type of AE and grade, and by the time of onset in relation to the first day of therapy. Attribution of AEs to treatment (unrelated, unlikely, possible, probable, or definite) will be recorded, and the details of all treatment-related toxicities will be reported.

### Survival

PFS will be measured from the initial date of treatment to the date of documented progression, or the date of death (in the absence of progression).

Overall survival will be measured from the initial date of treatment to the recorded date of death or for a total of 5 years follow up (See Section 12.3).

PFS and overall survival will be estimated by the Kaplan-Meier method. The corresponding median survival times (with 90% confidence limits) will be determined, as will the cumulative percentage of patients remaining progression-free at selected time points after initial treatment.

### Tumor Response

Response rates will be estimated by the proportion of patients with a best response of complete response (CR), partial response (PR), or stable disease (SD) by RECIST criteria, with corresponding exact 90% confidence limits being reported. The distribution of response duration (time to progression among patients

achieving CR, PR, or SD) will be characterized by median and quartiles, with the corresponding Kaplan-Meier estimate being made of PFS among patients responding to treatment.

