## Clinical Studies of Cetuximab in Head and Neck Cancer

The addition of cetuximab to radiation produced promising results in a phase I trial in patients with locally advanced head and neck cancer. Sixteen patients were treated with radiation therapy plus cetuximab. Cetuximab was delivered as a loading dose of 100 to 500 mg/m^2, followed by weekly infusions of 100 to 250 mg/m^2 for 7 to 8 weeks. There was one grade 4 allergic reaction. Most acute adverse effects were associated with radiation (xerostomia, mucositis, and local skin toxicity). All patients achieved an objective response (13 patients had a complete response). Based on these promising results, a phase III trial of radiation with or without cetuximab in stage III/IV head and neck cancer was conducted and recently reported results. The addition of cetuximab resulted in improved locoregional control and survival whereas the rate of mucositis was comparable between arms (see more details below). Based on the results of this study, cetuximab was approved by the FDA for the treatment of locally advanced SCCHN in combination with radiation and as monotherapy for patients with SCCHN who failed cisplatin-based chemotherapy.

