## 1.6 Phase I Trial of EGFR AS in Patients with Recurrent SCCHN

Previous studies have reported negligible toxicity following intratumoral administration of DNA. Our preclinical studies suggest that 60 µg of antisense DNA decreases tumor progression. Therefore, we implemented a rapid dose escalation (100% increment increase between tiers) in the phase I clinical study of EGFR AS. Eligible patients had recurrent SCCHN and have previously failed other treatments. Patients received weekly intratumoral injections for 4 weeks. The dose of EGFR AS was escalated in successive cohorts of patients (classic “3+3” design) as follows: level 1 - 60 µg/60 µL, level 2 - 120 µg/120 µL, level 3 - 240 µg/240 µL, level 4 - 480 µg/480 µL, level 5 - 960 µg/960 µL, and level 6 - 1.92 mg/1.92 mL. A total of 17 patients were enrolled. We reported results at the ASCO 2007 meeting. No grade 3 or 4 or any dose limiting toxicities were observed at any dose level. A dose of up to 1.92 mg/1.92 mL of EGFR AS was well tolerated. There were four adverse events related to EGFR AS in this trial. All events were grade 1 and included two episodes of injection site pain/swelling, one episode of edema and one episode of lethargy. No dose limiting toxicities were observed at any dose level. One patient developed dehydration that was thought to be unrelated to the drug injection. Five of 17 patients (29%) achieved an objective response: 2 patients had a complete response and 3 patients had a partial response. In order to demonstrate transfection of the EGFR AS gene into the tumors, we performed polymerase chain reaction (PCR) analysis on DNA extracted from pre- and post-treatment patient tissue specimens. We were able to detect EGFR AS in the tissue specimens taken two weeks after the last EGFR AS injection in both non-responders and responders. Moreover, we observed that STAT3 and EGFR expression levels at baseline correlated with efficacy outcomes. The final manuscript is in preparation.

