## 2. OBJECTIVES

- To evaluate the safety of the combination of intratumoral EGFR AS DNA with standard cetuximab and radiation.
- To evaluate the locoregional control (primary endpoint), in patients with locally advanced SCCHN treated with intratumoral EGFR antisense DNA combined with standard radiation plus cetuximab.
- To evaluate the toxicities associated with the above treatment.
- To evaluate other efficacy parameters, including the objective response rate, distant control and overall progression-free survival, and overall survival.
- To determine the effect of EGFR antisense therapy on EGFR and EGFR-related biomarkers. We will use reverse phase protein microarrays (RPPA) and immunohistochemical (IHC) analysis of tissue microarrays (TMA), on baseline and post-treatment tumor tissue, to determine the expression level and modulation of a panel of EGFR and EGFR-pathway related biomarkers, including (but not necessarily limited to) EGFR, pEGFR, Src, pMAPK, STAT3, pSTAT3, pSTAT5, pSTAT1, pAKT, p38, p21, p27, PARP, E-cadherin, p-ErbB3, and Ki67. We hypothesize that the baseline expression or modulation of one or more EGFR signaling proteins will correlate with objective response rate and locoregional control after combined modality treatment.
- To examine the transfection of the EGFR antisense gene therapy in vivo.

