### Cytology and Histology

Cytologic and histologic techniques can be used to differentiate between complete and partial response in rare cases (e.g., after treatment to differentiate residual benign lesions and residual malignant lesions in germ cell tumors). Cytologic confirmation of the neoplastic nature of any effusion that appears or worsens during treatment is required when the measurable tumor has met response or stable disease criteria.

*The pathologic response after biopsy or neck dissection post chemoradiotherapy will be recorded.*

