### 11.2 Secondary Clinical Endpoints

Clinical secondary endpoints in phase II include adverse events, in-field and out-field, objective response rate, distant PFS, overall PFS, and overall survival.

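### Section 11.6 estimates the response rate as CR+PR+SD, which is a disease-control rate, and gives no estimator for the objective response rate named as a secondary endpoint

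*Combined protocol and SAP*

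**What the plan says.** Section 11.2 lists among the phase II secondary endpoints "objective response rate, distant PFS, overall PFS, and overall survival". Section 2 includes the objective response rate among the other efficacy parameters. It also hypothesises that baseline expression or modulation of EGFR signalling proteins "will correlate with objective response rate and locoregional control after combined modality treatment". Section 11.5 plans to relate the biomarkers to "other efficacy parameters, such as objective response rate, PFS, and overall survival".

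The estimator is in section 11.6, Tumor Response. Response rates are to be "the proportion of patients with a best response of complete response (CR), partial response (PR), or stable disease (SD" by RECIST, with exact 90% confidence limits. The next sentence defines response duration as time to progression in the same three categories, and adds a corresponding Kaplan-Meier "estimate being made of PFS among patients responding to treatment".

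Section 8 adopts RECIST v1.1 and describes measurement methods, but does not define the objective response rate. No other section gives a CR+PR estimator.

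**The concern.** The endpoint that is named and the quantity that would be estimated are different. A rate that counts stable disease measures absence of progression as best response, whereas the objective response rate measures tumour shrinkage that meets the CR or PR criteria.

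Three results are affected:

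- **The rate.** The reported figure would exceed the objective response rate by the share of patients whose best response is SD.
- **Duration and responder PFS.** Both would include patients who did not respond.
- **Biomarker analyses.** The plan does not say whether response there means the section 11.6 definition or CR+PR. Two outcome definitions would be available for 16 listed markers, and the choice could be made after the data are seen.

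The result also could not be compared like for like with the response figures that the protocol itself cites.

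**Working it through.** **1. How the protocol itself counts objective response.** Section 1.6 reports that 5 of 17 phase I patients "achieved an objective response: 2 patients had a complete response and 3 patients had a partial response". (2 + 3)/17 = 0.294, which reproduces the stated 29% with no SD patient counted. A passing remark in section 8.1 (Cytology and Histology) also separates the two categories: "when the measurable tumor has met response or stable disease criteria". That sentence concerns confirmation of effusions and is minor support; section 1.6 carries the point.

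**2. Whether section 11.6 could mean one rate per category.** The plural in its opening words might suggest this. The following sentence pools the three categories for duration and then calls the corresponding group patients who respond. SD is therefore treated as response.

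**3. Size per patient.** With n = 31 (section 11.1), the difference between the two rates is (number with SD)/31, so 1/31 = 3.2 points for each SD patient. They agree only if no patient has SD as best response.

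**4. What the documents suggest about the number with SD.** They give no expected share. The nearest information is the phase I trial of radiation plus cetuximab in section 1.4, with 16 patients: "All patients achieved an objective response (13 patients had a complete response". The exact two-sided 90% lower limit for 16/16 is 0.05^(1/16) = 0.829. If that rate carried over, at most 1 − 0.829 = 17.1% of patients would lack an objective response, so the overstatement would lie between 0 and 17 points.

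**5. Illustration at n = 31.** Assume 2 patients progress as best response, so the section 11.6 rate is 29/31 = 93.5% in every row. Exact (Clopper-Pearson) 90% limits are the 0.05 quantile of Beta(x, n − x + 1) and the 0.95 quantile of Beta(x + 1, n − x). As a check of the method at 95%, 13/103 gives 12.6% (6.9% to 20.6%), which agrees with the 13% (7%-21%) in section 1.4; the count of 13 is inferred from that percentage. For 29/31 the 90% limits are 81.1% to 98.8%.

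| SD (assumed) | CR+PR | Rate | Exact 90% limits | Section 11.6 rate minus CR+PR |
|---|---|---|---|---|
| 0 | 29/31 | 93.5% | 81.1% to 98.8% | 0 points |
| 3 | 26/31 | 83.9% | 69.0% to 93.4% | 9.7 points |
| 7 | 22/31 | 71.0% | 54.8% to 83.9% | 22.6 points |
| 12 | 17/31 | 54.8% | 38.7% to 70.3% | 38.7 points |

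The last two rows lie beyond the 17-point limit from step 4. They show how the gap grows and are not a forecast.

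**6. Biomarker contrast.** Under the same assumption, a response outcome that includes SD would compare 29 patients with 31 − 29 = 2.

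**The case against.** The strongest reply is that this is loose naming rather than a redefinition. Section 11.6 speaks of response rates under a heading of additional analyses and does not use the term objective response rate. RECIST v1.1 is adopted in section 8, section 1.6 shows that the team counts CR+PR, and the categories entering the rate are spelled out, so nothing is hidden. CR+PR can be calculated at any time from the recorded data. No decision rule uses response, and the biomarker analyses are declared exploratory, with no test specified for response. The only relevant data in the documents suggest few SD patients.

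Much of this stands as a limit on the consequences. The expected gap may be small, and the larger scenarios are only assumed. It does not supply an estimator for the named endpoint. On any reading, the only written rule includes SD, and duration and responder PFS still pool SD patients.

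One further point stands. Sections 9.3, 9.4 (note 4) and 12.3.1 require clinical and radiographic response, and response in the primary and in the nodes, to be reported separately. Defining response as CR or PR therefore does not by itself say which assessment feeds the rate.

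**Conclusion.** The concern holds. Followed as written, section 11.6 would report a disease-control rate as the response rate, and the secondary endpoint in section 11.2 would have no matching analysis. The overstatement is 3.2 points per SD patient at n = 31. The total is unknown: it could be zero, and is at most about 17 points if the 16-of-16 result in section 1.4 carries over, which rests on a small earlier trial without EGFR AS. The effect is confined to a secondary, estimation-only endpoint, its duration summaries and the exploratory biomarker analyses. The primary endpoint of 1-year locoregional PFS and the 31 patients do not change. The correction should be made before response data are analysed.

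**What to change.** - In section 11.6, define objective response as a best response of CR or PR by RECIST v1.1, estimated with exact 90% limits in the population already specified, and say which assessment (clinical or radiographic, overall or by site) feeds it.
- Limit response duration and PFS among responders to CR/PR patients.
- Report CR+PR+SD separately, labelled as disease control.
- In section 11.5, add a cross-reference stating that the biomarker-response analyses use the CR+PR definition.

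The cost is the rewording of two sentences in section 11.6, including the choice of assessment, and one cross-reference in section 11.5. No new data are needed, because section 12.3.1 already requires response and serial measurements to be recorded. The stated response rate may be less favourable. No planned summary of the rate is lost, since CR+PR+SD is still reported under its proper name.

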## 5. TREATMENT PLAN

- Loading dose of cetuximab 400 mg/m^2 IV over 120 minutes 2 weeks prior to starting radiation.
- Cetuximab 250 mg/m^2 IV over 60 minutes weekly, the week prior and during days of radiation, until radiation is completed (diphenhydramine hydrochloride [Benadryl] premedication 30-60 minutes prior to cetuximab infusion as required, see 5.1).
- Intratumoral EGFR AS injections weekly x 7 weeks (or less if there is no identifiable tumor), starting 2 weeks prior to radiation and after cetuximab is administered. Subsequent EGFR AS injections can be given before or after cetuximab is administered. Injections will be in the primary and/or lymph nodes. One site will be injected per weekly session. The intratumoral EGFR AS injections should occur during the same calendar day due to CTRC scheduling. If it is necessary the antisense injection can be scheduled within 1 business day of the original schedule date and then resume the original schedule.
- EGFR AS will be administered by direct intratumoral injection using direct visualization, endoscopy, or imaging-guidance (ultrasound) as clinically determined. The same lesion (primary tumor or lymph node) will be injected during treatment.
- Radiation therapy 70 Gy, 200 cGy/daily, 5 days/week (see 5.3). Radiation will start on a Monday, Tuesday, or Wednesday. Cetuximab will be given prior to radiation.
- A tumor biopsy will be performed prior to starting cetuximab and 2 weeks later but prior to starting radiation.
- In the first stage, after three (3) subjects are enrolled and have received all EGFR AS injections, there will be a two-week waiting period to assess adverse events before enrolling additional subjects. After the two-week period, additional subjects may be enrolled.

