### 5.3.3 Radiation Dose

Treatment to the primary tumor and upper neck will be given at 2 Gy/fraction once each day, five days a week. A total dose of 70 Gy/35 fractions/7 weeks will be delivered. Fields must be reduced to exclude the spinal cord at 36 Gy with dose calculated in the central plane. The entire neck must be irradiated to a total dose of at least 46- 50 Gy (even in N0 stage) at anatomic levels of lymph nodes usually 2-4 cm beneath the skin surface. Clinically positive neck nodes should also receive a dose of 70 Gy/35 fractions given continuously for 7-8 weeks. An electron beam should be used to supplement the dose to the posterior cervical chain nodes after the spinal cord has been shielded. Hence, the total dose to the primary tumor and clinically positive nodes will be 70 Gy. The anterior lower neck will be treated at 2 Gy/fraction once a day (3 cm depth or at depth determined by 3D imaging) from the anterior to a total dose of 46-50 Gy/25 continuous fractions (if clinically negative) in 5 weeks. The maximum dose permitted to the spinal cord will not exceed 45 Gy as determined by a separate off-axis point dose calculation.

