#### After completion of radiation (10 +/- 2 weeks after)

- History and physical examination
- Complete blood counts, including platelets
- Blood chemistry studies, including creatinine, electrolytes (K+, Na+, Cl, CO2), Ca++, Mg++, ENT evaluation/endoscopy
- Liver function tests: Bilirubin, AST (SGOT), ALT (SGPT), and alkaline phosphatase
- CT and/or MRI of neck
- CT of chest
- Response assessment by clinical and by radiographic evaluation (reported separately) in primary and lymph nodes
- PET scan (optional)

After completing treatment, patients will be seen every 3 months for 2 years and then every 6 months for 3 years (i.e. until 5 years from radiation completion), and subsequently annually for a total of 10 years from study initiation (follow up evaluation will include assessment of late toxicities, such as dysphagia, G-tube feedings requirements, xerostomia, and others)

- CT scans of chest and head and neck will be performed every 3 months for 1 year and then every 6 months until 3 years from the completion of radiation. Then, CT of the chest will be done on an annual basis
- Swallowing assessments will be performed 3 months post radiation completion, and if problems persist, at 12 months post radiation

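### The responder PFS curve starts at first treatment, 15–21 weeks before the first scheduled response assessment, so its early part is essentially event-free by construction

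*Combined protocol and SAP*

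**What the plan says.** - **Start of PFS.** Section 11.6 (Survival): "PFS will be measured from the initial date of treatment to the date of documented progression", or to death if there is no progression. The documents give no other origin for PFS.
- **Who is a responder.** Section 11.6 (Tumor Response) counts patients with "a best response of complete response (CR), partial response (PR), or stable disease (SD) by RECIST criteria".
- **Responder analyses.** The following sentence begins "The distribution of response duration (time to progression among patients" and limits the group to CR, PR or SD. It does not say from which date duration is counted. It closes with the "Kaplan-Meier estimate being made of PFS among patients responding to treatment", and names no landmark or time-dependent method.
- **Treatment timing.** Section 5 gives the cetuximab loading dose "IV over 120 minutes 2 weeks prior to starting radiation". Section 5.3.3 states: "A total dose of 70 Gy/35 fractions/7 weeks will be delivered".
- **First response assessment.** The follow-up heading in Section 9.3 begins "After completion of radiation (10 +/- 2 weeks after", and that visit includes clinical and radiographic response assessment. Footnote 4 of the Section 9.4 table instead places tumor assessment 6–8 weeks after radiotherapy. The tumor-measurement row of that table has no entry in the on-treatment column.
- **Population.** Section 11.1 limits the efficacy-evaluable set to patients who complete the regimen, and Section 11.6 uses evaluable patients for response and survival.

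**The concern.** Membership of the responder group is settled at an assessment months after the PFS clock starts. A patient who progresses or dies before that assessment would not normally be classed CR, PR or SD, so early events drop out of the responder curve. This is guaranteed (immortal) time. The curve stays high over that period because of how the group is selected, whatever the treatment does.

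Counting SD as response makes the selection close to complete: the group is nearly everyone who has not progressed at the first assessment. Read beside the overall PFS curve, the responder curve would then mostly show the effect of having remained event-free that long, and could be taken for a benefit of responding.

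Response duration has a related gap. With no start date given, an analyst could count it from first treatment, from the assessment, or from first documented response, and the answers differ by months.

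**Working it through.** The plan states no figure for responder PFS or response duration, so there is none to reproduce on this point. The 1-year rates used below are the Section 11.1 design rates, and the sample size built on them does reproduce. With hazards −ln 0.68 = 0.3857 and −ln 0.83 = 0.1863 per year, 2 years of accrual and 1 year of follow-up, the probability of an observed event is p = 1 − (e^(−λ) − e^(−3λ))/(2λ), which is 0.526 and 0.307. Then N = [(1.2816/√0.526 + 1.2816/√0.307) / ln(0.3857/0.1863)]² = 31.4, with power about 0.90 at the planned 31.

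**Step 1: when response is first assessed, in weeks from first treatment**

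- Lead-in 2 weeks (Section 5), plus radiation 7 weeks (Section 5.3.3), makes 9 weeks.
- Section 9.3: 9 + 8 = 17 to 9 + 12 = 21.
- Section 9.4, footnote 4: 9 + 6 = 15 to 9 + 8 = 17.
- Range across the documents: 15–21 weeks.

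**Step 2: how much of this is new.** Completing the regimen takes about 9 weeks, and Section 7.8 removes patients who progress. The overall PFS curve in completers therefore already carries about 9 event-free weeks. The excess in the responder curve is 15 − 9 = 6 to 21 − 9 = 12 weeks.

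**Step 3: illustrative size at 1 year.** Assume exponential PFS with 1-year rate S and no prognostic difference for responders. Among patients event-free at week w, the 1-year value counted from first treatment is S^((52 − w)/52).

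| Underlying S | Completers, w = 9 | w = 15 | w = 17 | w = 21 |
|---|---|---|---|---|
| 0.68 | 0.727 | 0.760 | 0.771 | 0.795 |
| 0.83 | 0.857 | 0.876 | 0.882 | 0.895 |

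Unrounded, the last column is 0.7946 and 0.8949, hence 79% and 89%. A simulation of 2,000,000 exponential times gave 0.772 and 0.795 (S = 0.68), and 0.882 and 0.895 (S = 0.83), at weeks 17 and 21.

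**Step 4: median.** Under the same assumptions the median from first treatment is w plus the residual median, 52 × ln 2 / (−ln S), which is 93.5 weeks at 0.68 and 193.4 weeks at 0.83. Adding 15–21 weeks lengthens it by 16–22% (15/93.5 to 21/93.5) and 8–11% (15/193.4 to 21/193.4).

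**Step 5: after the change.** With the clock started at week w, the 1-year values return to 0.68 and 0.83, and the medians to 93.5 and 193.4 weeks.

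**The case against.** Several points on the other side are sound and limit the conclusion.

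- **Response duration.** A reader might infer that every reported duration is lengthened by 17–21 weeks. The documents do not support that. Section 11.6 sets a start date for PFS and overall survival but none for response duration. What can be said is that the start is undefined.
- **Strictly zero early events.** One might say that no responder can have an event before the assessment. That is firmer than the text. Section 8.1 allows the primary site to be evaluated by ENT examination, Section 9.2 requires weekly evaluation, and Section 5.2 ends injections once no tumor can be identified. Nothing says an earlier clinical observation cannot count. The first *scheduled* response assessment is still after radiation, so the curve is essentially, not strictly, flat until then.
- **Baseline.** Treating all 15–21 weeks as excess over the overall PFS curve ignores the completer-only population.
- **Design rates.** The 68% and 83% are locoregional rates, whereas PFS in Section 11.6 ends at progression or death.
- **Comparison with published durations.** The documents do not show what start date outside durations use. Section 1.4 quotes a median response duration of 5.8 months for cetuximab alone without giving its origin.
- **Importance.** This is a descriptive additional analysis, no test of responders against non-responders is planned in that section, and a PFS curve counted from first treatment does follow the plan's own definition.

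The selection itself remains: the responder curve has an explicit origin at first treatment, and no landmark is given.

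**Conclusion.** The concern holds as a minor point about a descriptive analysis. Followed as written, Section 11.6 produces a responder PFS curve with 15–21 weeks of essentially guaranteed event-free time, about 6–12 weeks more than the overall PFS curve in treatment completers. Those weeks follow from the schedule, taking a 7-week radiation course.

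The percentages are illustrations: an underlying 68% at 1 year would read about 76–79%, and 83% about 88–89%. They rest on exponential PFS, no prognostic difference for responders, and locoregional rates standing in for PFS.

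For response duration the defect is a missing start date. Only if it takes the PFS origin does it carry the same 15–21 weeks.

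A reader might go further and doubt the phase II result. The documents do not support that: the primary test, alpha, power and the 31 patients do not use the responder curve.

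**What to change.** In Section 11.6 (Tumor Response), state that the responder Kaplan-Meier curve and response duration both start at a common landmark, the first post-radiation response assessment, and include patients who are event-free and classed CR, PR or SD at that time. Duration from the date of first documented response may be reported in addition, for CR and PR only, because SD has no such date.

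Reconcile Section 9.3 with footnote 4 of the Section 9.4 table on when that assessment takes place, since the landmark depends on it.

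The cost is a sentence or two in Section 11.6 and that reconciliation. No further patients or visits are needed, since the serial measurements are already collected under Section 12.3. The reported duration and responder curve will be shorter and less favourable. The primary analysis and sample size do not change.
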